4.2 Treatment Period

Patients who are not taking metformin at the time of study enrollment will receive oral metformin extended release (Glucophage® XR, 750 mg tablets). Metformin is to be taken with a meal as one 750-mg pill per day for the first 4 days, followed by two 750-mg pills per day (one pill in morning, one pill in evening), for a total pre-surgical metformin regimen of 7-10 days (as depicted in schematic above). The last dose of metformin extended release should be taken at 7:00 pm (+/- 1 hour) the night preceding the surgery.

Patients already taking metformin for a clinical indication at the time of study enrollment will continue their metformin regimen while on study. The last dose of metformin should be taken the night preceding the surgery. A record will be kept regarding which patients are not taking the 750 mg BID dosing of metformin and this will be noted in the analysis.

All patients will record the dates and times of metformin ingestion on the evening before surgery in a drug diary.

A single patient who has not been treated with metformin will be consented and enrolled. This patient will be asked to provide tumor, adipose, normal lung tissue, and blood samples, and all samples will be collected as described in section 4.2.2. These samples will be taken to serve as a control and are needed in order to optimize the metformin quantification.

4.2.1. *Presurgical metformin*

Patients enrolled will be treated with metformin (administered orally; 750 mg QD for 4 days, then 750 mg BID for 3-6 days; or clinically indicated metformin) for a total of 7-10 days prior to surgery, up until the night before surgery.

4.2.2. *Surgery and biological specimens*

Specimens will be acquired and processed as described in Appendix A.

Plasma and Whole Blood

On the morning of surgery, 20 mL of blood will be collected for research purposes in the pre-operative area. This blood may be collected at the same time as a routine clinically indicated blood draw or during placement of an intravenous line (before saline is administered), and should occur as close to the time of surgery as possible. Blood will be drawn into (2) 10-mL purple-top (EDTA-treated) tubes, picked up by a member of the [name] Lab within 1 hour of being drawn from the patient, and processed by the [name] Lab as in Appendix A.

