In the [name] Lab, a 10-mL blood sample will be centrifuged at 1,000 x g for 30 minutes at 4°C to separate plasma, which will be aliquoted into cryovials (1 mL/vial). The other 10-mL blood sample will be aliquoted into cryovials (1 mL/vial) as whole blood. All plasma and whole blood sample aliquots will be stored at -80°C until analysis.

Tumor tissue, adipose tissue, and normal adjacent tissue

Requested specimens: Tumor tissue fragment ≥ 8 mm in diameter*

Adipose tissue fragment ≥ 8 mm in diameter*

Normal adjacent tissue fragment ≥ 8 mm in diameter*

* small tissue fragments may be pooled to yield ≥ 8 mm of tissue

The patient will undergo surgical resection or biopsy of the tumor(s). During the procedure, the surgeon will attempt to obtain a sample (≥ 8 mm in diameter) of adipose tissue (likely subcutaneous) and normal adjacent tissue (such as lung, when available) (≥ 8 mm in diameter) when feasible.

All normal and tumor tissues will be sent to Pathology for dissection. The Pathologist or her/his designate will promptly dissect the surgical specimen(s). ASCO-CAP guidelines require initiation of dissection of a surgical specimen within 1 h of removal from the patient; for this study, minimal lag time (“cold ischemia time”) is preferred.

The Pathologist will assess whether the tumor specimen is large enough to procure:

- A. tissue for routine diagnostics.
- B. ≥ 6 tumor fragments that are ≥ 4 mm³ in all dimensions for research use.

A 1.5-cm tumor is expected to provide sufficient material for all needs.

If the tumor is too small to provide adequate tissue for research, the tumor will be considered non-evaluable and the patient will need to be replaced.

Tissue specimens procured for research purposes will be cut into 4-mm³ fragments, weighed, and individually frozen in cryovials by a member of the [name] lab. Tissue specimens with overt blood content will be pressed between absorbent towels to remove blood prior to weighing. Please see SOP in Appendix A for tissue handling/processing and storage.

All research tissue samples should be frozen within 1.5 h of tissue removal from the patient; a shorter lag time is strongly preferred to preserve phospho-proteins.

4.2.3. *Metformin drug information*

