4.5 Analyses

1. *Pharmacokinetic analysis of metformin concentrations in plasma, whole blood, and tissues.*

The concentrations of metformin in all samples of blood, plasma, and tissue (tumor, normal, adipose) will be measured by a liquid chromatography (LC) with tandem mass

spectrometry (MS/MS) assay developed in the NCCC Clinical Pharmacology Shared Resource. The average value from the technical triplicates for each biological specimen will be used for calculations. This methodology is established in the NCCC Clinical Pharmacology Shared Resource for measurement of metformin concentrations in mouse tissues/tumors and cultured cells; this methodology will be re-optimized for analysis of human tissues using specimens collected from the single control subject enrolled in this study, in which specimens will be spiked with metformin to generate standard curves

In brief, the current assay consists of plasma protein precipitation using acetonitrile, and filtration over Phenomenex iPhree cartridges. The eluate is dried under nitrogen, resuspended in water, and injected into the LC-MS/MS. In mouse plasma (without full validation), assay accuracy was 91-98%, precision was <15% CV, and recovery was 89%.

2. *Immunohistochemical analysis of AMPK activity of pre- vs. post-metformin treated tumors.*

The goal of this exploratory endpoint is to determine whether metformin treatment alters phosphoprotein markers of AMPK activity in tissues.

In eligible patients, baseline (diagnostic biopsy specimen) and post-metformin (surgical specimen) tumor/normal tissue samples will be sectioned and processed for IHC in the NCCC Pathology Shared Resource. Tissue sections will be immunostained using antibodies against P-ACC(S79), and P-S6(S240/244). P-ACC and P-S6 will be scored using a Histoscore scale (36) that incorporates staining intensity and frequency. We expect metformin treatment to increase P-ACC and decrease P-S6 Histoscores, as metformin treatment should increase AMPK activity.

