8.0 STATISTICAL CONSIDERATIONS

8.1 PRIMARY ENDPOINT – Concentrations of metformin in tumor tissue.

8.2 SECONDARY ENDPOINT – Concentrations of metformin in adipose tissue, tumor-adjacent normal tissue, plasma, and whole blood.

8.3 EXPLORATORY ENDPOINT – Changes in AMPK activity induced by metformin, as determined by changes in P-ACC and P-S6 histoscores between pre- and post-metformin tissue specimens.

8.4 PRIMARY ANALYSIS PLAN – The primary analysis will measure the concentrations of metformin in biological triplicate samples of plasma, whole blood, and tissue specimens from each patient. Metformin concentrations will then be statistically analyzed to determine A) variability between biological triplicates, B) inter-individual variability between patients (within each tissue type; calculate descriptive statistics), and C) relationships between tissue types within each patient (compared by paired *t*-test or two-way ANOVA).

8.5 EXPLORATORY ANALYSIS PLAN – An exploratory analysis will determine whether metformin treatment significantly alters AMPK signaling in tumors compared to baseline. Histoscores from paired (pre- and post-metformin) tissue specimens will be compared by Wilcoxon rank sum test, and the correlation with metformin concentration will be established (the log transformation may be used to comply with the normal distribution assumption). Furthermore, an exploration of the metformin concentrations in plasma blood and tumor tissue and changes in tumor Histoscores will be undertaken using the direct PK-PD model (e.g., sigmoid Emax).

8.6 STATISTICAL TESTING - All statistical tests will be two-sided, and the overall type I error will be 0.05.

8.7 SAMPLE SIZE – We propose to evaluate 20 patients for the Primary Endpoint to account for the wide range (>75-fold) of steady-state plasma concentrations of metformin previously shown in

humans (12). There are no data on intra-tumor concentrations of metformin. As a surrogate, we will use plasma concentrations of metformin under the assumption that plasma and tumors will exhibit similar ranges of variability between patients. We will enroll one additional subject to acquire control tissues, bringing the total study accrual goal to 21 subjects.

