Appendix A

Standard Operating Procedure for Fresh Tissue Acquisition by Surgery and a Blood Sample (D17188- presurgical metformin study)

1) Consent

The patient will be asked to provide informed consent by a treating surgeon, oncologist, or designated personnel at a presurgical consultation visit.

The personnel obtaining consent will notify the CRC [[name] ([contact])] that a patient has been consented, and the CRC will pick up Consent Form.

The CRC will register the patient into the research database (Velos), and give the patient a unique research identification number (ID#):

“D17188_###” starting with D17188-001 as patient 001.

2) Blood specimen (day of surgery; prior to surgery)

20 mL of venous blood (ideally, in two 10-mL tubes) will be obtained prior to surgery (as close to the time of surgery as possible) in the pre-operative area, which may be done during a routine pre-surgical blood draw or placement of an i.v. line.

Blood should be collected in **purple-top (EDTA) tubes** labeled with the patient’s name and time of draw.

The person drawing the blood will immediately notify the [name] Lab that the blood specimen is ready for pick-up. A [name] Lab member will pick up the specimen within 1 hour from the Operating Room (OR) Control Desk (located on the 4th floor near the ICU).

[name] Lab e-mail: [contact]

(preferred) [name] Mobile [contact]

[name] Lab [contact]

[name] Office [contact]

In the [name] Lab, one 10-mL sample of blood will be aliquoted into cryovials (1 mL/vial, approx. 10 vials) and frozen at -80°C as **whole blood**.

One 10-mL sample of blood will be centrifuged at 1,000 x g for 30 min at 4°C (metformin is stable), and **plasma** (supernatant) will be aliquoted into cryovials (1 mL/vial, approx. 5 vials) and frozen at -80°C.

3) Tumor, adipose, and normal tissue specimens (by surgery)

The CRC will notify [contact] with **maximal advance notification** of the date of surgery. The CRC will notify the Pathology Department individuals and [name] Lab individuals listed below 24 hours prior to the time of surgery with notice that a surgical specimen will be arriving and that tissue is to be acquired for this study to **minimize time between surgery and freezing**.

The surgical specimen may provide a diagnostic specimen; excess tissue will be used for research purposes.

Pathology Dept. e-mails: [contact]

[contact]

[name] Lab: [contact]

(preferred) [name] Mobile [contact]

[name] Lab [contact]

[name] Office [contact]

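### Section 8.4 calls plasma and whole-blood aliquots biological triplicates, and does not fix the unit of analysis for its two-way ANOVA

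*Combined protocol and SAP*

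**What the plan says.** Section 8.4 sets the replicate structure for every matrix: "The primary analysis will measure the concentrations of metformin in biological triplicate samples of plasma, whole blood, and tissue specimens from each patient". The first output it names is "A) variability between biological triplicates". Output (B) is inter-individual variability within each tissue type. Output (C) compares tissue types within patients, by paired t-test or two-way ANOVA.

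Collection is described in section 4.2.2. "On the morning of surgery, 20 mL of blood will be collected for research purposes in the pre-operative area", and "Blood will be drawn into (2) 10-mL purple-top (EDTA-treated) tubes". One tube is centrifuged "to separate plasma, which will be aliquoted into cryovials (1 mL/vial"). For the second tube: "The other 10-mL blood sample will be aliquoted into cryovials (1 mL/vial) as whole blood". Appendix A, item 2, repeats this: "In the [name] Lab, one 10-mL sample of blood will be aliquoted into cryovials (1 mL/vial, approx. 10 vials"), with about 5 plasma vials from the other tube.

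Tissue is handled differently. Section 4.2.2 and Appendix A, item 3, ask for at least 6 separately cut tumor fragments, and tissue fragments are stored one per vial.

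Section 4.5 uses another replicate term: "The average value from the technical triplicates for each biological specimen will be used for calculations". No section says how those technical triplicates relate to the biological triplicates of 8.4.

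**The concern.** Three vials filled from one tube are three portions of one sample. Any difference among them comes from pipetting, storage and the assay. Reported under 8.4(A) as biological variability of plasma or whole blood, the figure would carry a wrong name, and a reader could take assay precision for pharmacological stability.

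The same ambiguity reaches 8.4(C). Each patient contributes several matrices, and each matrix contributes three values. The independent unit for a tissue comparison is the patient, so the right yardstick is how much the tissue difference varies between patients. A two-way ANOVA fitted to all the replicate values can instead use the replicate spread as its error term. It then treats patient-to-patient differences in tissue uptake as evidence of a mean tissue effect. The overall type I error of 0.05 in section 8.6 would not hold under that analysis, which 8.4(C) does not rule out.

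**Working it through.** **1. The plan's own figure.** Section 8.7 gives n=20, null CV 25%, detectable CV 15%, 90% power, one-sided alpha 5%. A lower-tail chi-square test of a variance on 19 df has power P(χ²₁₉ ≤ χ²₁₉(0.05) × (0.25/0.15)²) = P(χ²₁₉ ≤ 10.117 × 2.778 = 28.10) = 91.8%. The minimum detectable CV is 0.25 × √(10.117/27.204) = 15.25%. With log-scale SD √ln(1+CV²) the power is 90.8%. The figure reproduces. It concerns between-patient tumor CV and uses no replicate variance, so this point does not touch it.

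**2. What aliquots can estimate.** Write a log concentration as patient effect + within-patient biological effect w (SD σ_w) + assay-and-handling error e (SD σ_e). Three aliquots of one tube share the same w, so their SD is σ_e whatever σ_w is. Three separately taken samples would have SD √(σ_w² + σ_e²). The documents give no σ_w. For the assay, section 4.5 gives only a CV below 15%, in mouse plasma without full validation. Both SDs below are therefore assumptions:

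| σ_e | σ_w | SD of aliquots | SD of separate samples |
|---|---|---|---|
| 0.15 | 0 | 0.15 | 0.15 |
| 0.15 | 0.10 | 0.15 | 0.180 |
| 0.15 | 0.20 | 0.15 | 0.250 |
| 0.15 | 0.30 | 0.15 | 0.335 |
| 0.05 | 0 | 0.05 | 0.05 |
| 0.05 | 0.10 | 0.05 | 0.112 |
| 0.05 | 0.20 | 0.05 | 0.206 |
| 0.05 | 0.30 | 0.05 | 0.304 |

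The aliquot column does not move with σ_w, so the planned blood samples carry no information on it.

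**3. Replicate-level two-way ANOVA.** Assume no true mean tissue difference, n=20 patients, r=3 replicates, T tissues, patient-by-tissue SD σ_pt, and the same replicate SD σ_e in every matrix. The tissue mean square has expectation σ_e² + rσ_pt², and the replicate mean square has expectation σ_e². With k = 1 + rσ_pt²/σ_e², the rejection rate is P(F > F_crit/k) on T−1 and nT(r−1) df. For two tissues the df are 1 and 80 (F_crit 3.96). For five matrices they are 4 and 200 (F_crit 2.42).

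Example: σ_e = σ_pt = 0.15 gives k = 1 + 3 = 4, and P(F₁,₈₀ > 0.99) = 32%.

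Rejection rate, two tissues / five matrices:

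| σ_e | σ_pt = 0 | σ_pt = 0.15 | σ_pt = 0.30 | σ_pt = 0.50 |
|---|---|---|---|---|
| 0.05 | 5% / 5% | 71% / 99% | 85% / 100% | 91% / 100% |
| 0.15 | 5% / 5% | 32% / 66% | 58% / 95% | 74% / 99% |
| 0.30 | 5% / 5% | 14% / 24% | 32% / 66% | 52% / 90% |
| 0.50 | 5% / 5% | 8% / 11% | 17% / 33% | 32% / 66% |

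**4. Additive model.** Leaving out the interaction pools it with replicate error (19 + 80 = 99 error df for two tissues, 76 + 200 = 276 for five). Over the same non-zero grid, simulated rejection runs from about 7% to just under 40% for two tissues, and from about 9% to just over 60% for five matrices.

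**5. One value per patient per matrix.** Tissue is then tested against the patient-by-tissue term. Numerator and denominator both scale with k, so the rate is 5% in every cell. A paired t-test on patient values is the two-tissue case.

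**The case against.** The strongest reply is that this is mostly a label. A triplicate variance for plasma and blood can be computed, and it is a useful precision figure. Once the blood vials are recognised as technical replicates, the averaging sentence in 4.5 already reduces them to one value per patient. The paired t-test is listed first in 8.4(C), and a two-way ANOVA on patient means is also valid and fits the wording. The rejection rates depend on SDs that the documents do not give. Fragment replicates would add real heterogeneity to the replicate SD, which lowers the inflation.

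Most of this stands, and it rules out several stronger readings:

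- A reader might infer that 8.4(A) cannot be carried out for blood. It can; the result is simply not what its name says.
- A reader might infer that tumor will be made to look heterogeneous beside blood. No section plans to compare replicate spread across matrices, and 8.4(A) does not carry the words about each tissue type that (B) does.
- A reader might infer that the plan commits to an invalid ANOVA. It does not specify one.

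Two things remain. The label in 8.4 contradicts the collection procedure. And the averaging rule in 4.5 covers technical triplicates only, so for tissue fragments nothing says whether 8.4(C) uses three values per patient or one.

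**Conclusion.** The labelling error is certain on the documents' own text: plasma and whole blood each come from one tube of one draw, and their replicate spread is assay-plus-handling error. The note in Appendix A that two tubes are the ideal adds no replicate tube for either matrix.

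The ANOVA point is conditional. If replicate values enter as observations, type I error exceeds 5% whenever patient-by-tissue variation is present. Over the assumed SDs the excess ranges from slight (8%) to near-certain rejection. No single figure from that range is a property of this plan, and the grid assumes equal variances across matrices.

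It would be wrong to extend this to the primary endpoint or the sample size. Tumor is collected as separate fragments, plasma and whole blood are secondary endpoints under 8.2, and the power statement in 8.7 stands. The text should be corrected before analysis; the design need not change.

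**What to change.** In section 8.4:

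- Call the plasma and whole-blood replicates technical aliquots, average them under the 4.5 rule, and report their CV as assay-plus-handling error.
- Limit 8.4(A) to fragments of tumor, normal and adipose tissue.
- For 8.4(B) and (C), state that each patient contributes one value per matrix, the mean of its replicates or fragments. Alternatively, treat patient as a random block and test tissue against the patient-by-tissue term.
- Add a sentence to 4.5 or 8.4 saying how technical and biological replicates relate for each matrix.

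This costs wording only: no new samples, patients or visits. P-values for tissue comparisons may be less favourable than a replicate-level ANOVA would have given.

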The log chi-square test is used to find the minimum detectable coefficient of variation [CV=relative standard deviation (SD)] for metformin in tumor tissues with $n=20$ sample size (number of tumors and patients). To compute the power of the test, we use the fact that the CV is approximately equal to SD on the log scale. Our one-sided power analysis implies that with $n=20$, under the null hypothesis that $CV=SD/\text{mean}=25\%$, the minimum detectable $CV=15\%$ with 90% power and the Type I error alpha=5%.

Based on the high number of patients undergoing surgical resection of lung tumors at DHMC, we project that this study will complete accrual within 24 months.

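### Section 8.4C does not say how the biological triplicates enter the between-tissue tests or which ANOVA error term applies; used as three separate values, they would break the 5% level in 8.6.

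*Combined protocol and SAP*

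**What the plan says.** Section 8.4 states that the primary analysis will "measure the concentrations of metformin in biological triplicate samples of plasma, whole blood, and tissue specimens from each patient". The resulting concentrations feed three analyses. The first two are "A) variability between biological triplicates, B) inter-individual variability between patients (within each tissue type; calculate descriptive statistics"). The third is "relationships between tissue types within each patient (compared by paired *t*-test or two-way ANOVA").

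Section 4.5 gives the only averaging rule: "The average value from the technical triplicates for each biological specimen will be used for calculations". That leaves one value per biological specimen.

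Section 8.6 sets the error rate: "All statistical tests will be two-sided, and the overall type I error will be 0.05". Section 8.7 sizes the primary CV test "with $n=20$ sample size (number of tumors and patients").

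No section states whether the biological replicates are averaged before analysis C, what the unit of analysis in C is, whether patient is a random effect, or which mean square is the ANOVA denominator. There is also no rule for choosing between the t-test and the ANOVA.

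**The concern.** The patient is the independent unit. Three fragments of one tumor, or three aliquots of one blood tube, share that patient's absorption, transport and sampling time. They say little about how the tissue difference varies from patient to patient.

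Read in sequence, 4.5 and 8.4 deliver three values per patient and matrix to analysis C. A standard patient-by-tissue ANOVA with three values per cell tests the tissue effect against within-cell error. When patients differ in their tissue-to-tissue ratios, the right yardstick is the patient-by-tissue variation, which is larger. A t-test on 60 replicate pairs has the same fault, because it counts each patient three times.

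At stake is whether a reported difference between tumor and normal tissue, adipose tissue or blood can be trusted at the level 8.6 promises. Section 1.2 stresses large variability between patients and transporter-mediated distribution, so a patient-by-tissue component of zero is hard to assume.

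**Working it through.** **The plan's own figure first.** Section 8.7 gives 90% power for null CV 25%, true CV 15%, n = 20 and one-sided alpha 5%. Taking the CV as the log-scale SD, power = P(χ²₁₉ < χ²₁₉,₀.₀₅ × (0.25/0.15)²) = P(χ²₁₉ < 10.117 × 2.778) = P(χ²₁₉ < 28.10) = 91.9%. With the exact log-SD it is 90.8%. The stated 90% is reproduced with 20 patients as the unit, so the present point does not touch it. The 0.05 in 8.6 is a target with no calculation behind it.

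**Inputs from the documents.** Patients n = 20 (8.7); biological replicates r = 3 (8.4); two-sided alpha 0.05 (8.6); matrices k = 2 for one comparison, or k = 5 for tumor, normal tissue, adipose tissue, plasma and whole blood (2.1, 2.2).

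**Assumptions.** The documents give no variance components. Let s_pt be the patient-by-tissue SD and s_w the replicate SD, both on the log scale. I fix s_w at 0.15 and take s_pt = 0.05, 0.10, 0.15 and 0.25. The share of variance due to patient-by-tissue is ρ = s_pt²/(s_pt² + s_w²) = 0.10, 0.31, 0.50 and 0.74. There is no true tissue difference.

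**Two-way ANOVA with within-cell error.** The expected tissue mean square exceeds the within-cell mean square by the factor λ = 1 + r·s_pt²/s_w². The rejection rate is P(F > F_crit/λ), with k−1 and nk(r−1) degrees of freedom.
- k = 2: 1 and 80 df, F_crit = 3.96.
- k = 5: 4 and 200 df, F_crit = 2.42.
- Example, s_pt = 0.15: λ = 1 + 3 × 0.0225/0.0225 = 4. For k = 2, P(F > 0.99) = 32%; for k = 5, P(F > 0.60) = 66%.

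**Paired t-test on 60 pairs.** Simulated, and checked against 2 × [1 − Φ(1.96/√(1 + 2ρ))]. At ρ = 0.5 this is 2 × [1 − Φ(1.386)] = 16.6%.

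Type I error (nominal 5%):

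| s_pt / s_w | λ | Paired t, 60 pairs | ANOVA, 2 tissues | ANOVA, 5 matrices | Paired t, 20 patient means |
|---|---|---|---|---|---|
| 0.05 / 0.15 | 1.33 | 7% | 9% | 13% | 5% |
| 0.10 / 0.15 | 2.33 | 12% | 20% | 39% | 5% |
| 0.15 / 0.15 | 4.00 | 17% | 32% | 66% | 5% |
| 0.25 / 0.15 | 9.33 | 22% | 52% | 90% | 5% |

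An additive ANOVA (patient plus tissue, no interaction) falls in between: about 8-30% for two tissues and 10-50% for five matrices over the same range.

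**Limits.** At ρ = 0 every version holds about 5%. Keeping all replicates but testing tissue against the patient-by-tissue interaction gave 4.5-5.3% for ρ from 0 to 0.9. Averaging is therefore one valid remedy, not the only one.

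**The case against.** A reader might infer that the plan is pseudo-replicated as written and that its 5% level certainly fails. The documents do not support that. Section 8.4 is silent on the data layout of C, and nothing in 4.5 forbids a second averaging step.

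Several features fit a patient-level analysis. Replicate variability has its own analysis (A). Analysis C concerns "C) relationships between tissue types within each patient". The natural pair is one patient's two tissues, and no rule matches a given tumor fragment to a given adipose fragment. A two-way ANOVA with one value per cell uses the patient-by-tissue residual as its error and, for two tissues, equals the paired t-test, so offering the two as alternatives is coherent. Section 8.7 counts patients, although that sentence concerns only the CV test.

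The size is also conditional. The SDs are assumed. The largest figures need uncollapsed data, within-cell error and five matrices with equal variances. Plasma and whole-blood replicates are aliquots of single tubes (4.2.2, Appendix A), so one replicate SD for all matrices is a simplification.

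Finally, the secondary objective is to determine concentrations, no decision rule rests on C, and no confidence intervals are specified for it.

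All of this stands, and it limits both wording and severity. It does not remove the gap: two analysts could follow 8.4 faithfully, one with a valid test and one without.

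**Conclusion.** The point holds as an unspecified unit of analysis and error term with a material consequence. If the three biological replicates enter C as they stand, type I error is about 7-22% (paired t-test), 9-52% (two-tissue ANOVA) or 13-90% (five-matrix ANOVA) under the assumed SDs. It approaches 5% only as patient-by-tissue variation approaches zero. With one value per patient and matrix, or the interaction as denominator, it is about 5%.

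It would go too far to conclude that the primary result is compromised: the CV test and its 90% power are unaffected. Severity is should-fix, because the tissue comparison sits in the primary analysis plan but is not the primary CV objective.

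**What to change.** Add to 8.4: *Biological replicates (tissue fragments or blood aliquots) are averaged on the log scale to one value per patient per matrix before any between-matrix test. Alternatively, a mixed model with random patient and patient-by-tissue effects is fitted, and the matrix effect is tested against patient-by-tissue variation. Replicate-level values are used only for analysis A.* Choose one of the two in advance, and state in 4.5 and 8.4 how the technical and biological triplicates relate.

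The mixed model has the further merit of keeping patients who lack adipose or normal tissue, which 4.2.2 makes likely because those samples are taken only where feasible.

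The cost is a few sentences and no new data. The downside is that p-values may be less favourable than under a replicate-level analysis.

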2.0 OBJECTIVES

2.1 Primary Objective

To determine the intra-tumor concentrations of metformin, with a standard deviation $\leq 25\%$ of the mean, in patients with solid tumors of thoracic origin administered metformin extended release.

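### Objective 2.1 limits tumor SD to 25% of the mean, but the primary analysis (8.4) does not carry the one-sided test behind the power statement in 8.7, and 8.6 makes all tests two-sided

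*Combined protocol and SAP*

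**What the plan says.** Four places in the combined protocol and SAP bear on this point.

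- **2.1 Primary Objective** attaches a numerical limit to the primary aim: "To determine the intra-tumor concentrations of metformin, with a standard deviation" no larger than 25% of the mean.
- **8.4 Primary Analysis Plan** has three parts: (A) variability between triplicates, (B) "inter-individual variability between patients (within each tissue type; calculate descriptive statistics", and (C) comparisons between tissue types by paired t-test or two-way ANOVA. None refers to 25%.
- **8.6 Statistical Testing**: "All statistical tests will be two-sided, and the overall type I error will be 0.05". No exception is listed.
- **8.7 Sample Size** first justifies 20 patients by the more than 75-fold range of plasma concentrations. It then says "The log chi-square test is used to find the minimum detectable coefficient of variation" at that n. The scale is the log scale ("we use the fact that the CV is approximately equal to SD on the log scale"), the null is CV = 25%, and the direction is explicit: "Our one-sided power analysis implies that with" n = 20 the minimum detectable CV is 15%, at 90% power and alpha 5%.

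Sections 4.5 and 8.1 describe the assay and the endpoint and add no criterion for the 25% limit.

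**The concern.** The test that supports the power statement is absent from the analysis plan. Section 8.4 B will produce a tumor SD and mean, but nothing says what observed value meets 2.1. Two readings are open: the observed CV is at or below 25%, or the 8.7 test rejects CV = 25%. An observed log SD between about 0.18 and 0.25 meets the first and fails the second, so the answer on the primary objective could be settled after the data are seen.

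There is also a direct conflict if the test is run. Section 8.7 is one-sided and 8.6 allows only two-sided tests. The quoted 90% power depends on the one-sided form.

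**Working it through.** **Inputs.** n = 20, null CV 25%, alternative CV 15%, one-sided alpha 5%, power 90% (8.7); two-sided 0.05 (8.6); limit 25% (2.1); plasma range 54–4133 ng/mL (1.2). The test is taken as a lower-tail chi-square test on the variance of log concentration with df = 19. Quantiles of chi-square(19): 5% = 10.117; 2.5% = 8.907; 90% = 27.204.

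**1. Reproduce 8.7 (one-sided).** Power = P(χ²₁₉ < 10.117 × r).
- With CV = log SD, r = (0.25/0.15)² = 2.778 and power is 91.9%.
- With exact lognormal conversion, r = ln(1.0625)/ln(1.0225) = 2.725 and power is 90.8%.
- Minimum detectable CV = 25% × √(10.117/27.204) = 15.2% (15.1% exact).

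The stated 15% and 90% hold.

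**2. The same test under 8.6 (equal-tailed two-sided, 2.5% in the lower tail).**
- Power at CV 15% = P(χ²₁₉ < 8.907 × r) = 83.1% (81.4% exact).
- Minimum detectable CV = 25% × √(8.907/27.204) = 14.3% (14.2% exact).

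**3. Cut-offs on the observed log SD.**
- One-sided: 0.25 × √(10.117/19) = 0.182. The one-sided 95% upper bound is the observed log SD × √(19/10.117) = observed × 1.370, so an upper bound below 0.25 is the same rule.
- Two-sided: 0.25 × √(8.907/19) = 0.171.

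**4. How far the two readings of 2.1 differ.** Point-estimate pass = P(χ²₁₉ ≤ 19 × (0.25/true)²). One-sided test pass = P(χ²₁₉ < 10.117 × (0.25/true)²). The ranges cover CV = log SD and exact conversion; the point-estimate column also covers a lognormal simulation of raw SD/mean (400,000 runs).

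| True CV | Observed CV ≤ 25% | One-sided 8.7 test |
|---|---|---|
| 15% | >99.9% | 91–92% |
| 20% | 94% | 32–33% |
| 25% | 54–57% | 5% |
| 30% | 17–21% | 0.6% |

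**5. If tumors vary as plasma does.** ln(4133/54) = 4.338. Assume the range spans 4 to 6 SDs; the documents do not say. The log SD is then 1.08 to 0.72. The pass probability is at most 1.1 × 10⁻⁶ for the point estimate and 4.3 × 10⁻⁹ for the test, so both readings fail.

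**6. Cost of the CV = log SD approximation.** An exact lognormal CV of 25% has log SD √ln(1.0625) = 0.246. Testing against 0.25 then has type I error P(χ²₁₉ < 10.117 × 0.0625/0.0606) = 5.8%.

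**The case against.** The best case for the plan has three parts.

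- **The test is already specified.** 8.7 gives the test, scale, null, direction and alpha in the same Section 8.0 as 8.4, and the cut-off follows by arithmetic. Descriptive statistics do not contradict it; they supply the SD and mean that 2.1 names. This stands in part: between 8.4 and 8.7 there is an omission, not a contradiction. But a test used only to find a detectable CV is not a commitment to run it, and 8.6 would change it if it were run.
- **The documents point to wide variability.** 8.7 assumes tumors vary as plasma does, 1.2 gives bioavailability of 55% ± 16%, and 3.3 admits patients on any dose of metformin. If the true CV is well above 30%, the two readings agree. This stands and limits the consequence. It does not remove it, because 8.7 says there are no intra-tumor data and states its own power at a CV of 15%.
- **No stopping, dosing or go/no-go decision uses the 25% limit.** This also stands, and it keeps the severity low.

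A reader might infer that n = 20 was derived from the test, so that the sample size rests on an analysis that will not be done. The text does not support that: 8.7 first justifies 20 by the plasma range and then finds the detectable CV for that n. It is the test behind the power statement, not the rule that fixed n. Nor is the power figure wrong; it reproduces for the one-sided test.

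**Conclusion.** The point holds as an omission in 8.4 together with a conflict of sidedness between 8.6 and 8.7. Followed as written, the plan either judges 2.1 on a point estimate with no error control (met 54–57% of the time at a true CV of 25%, against 5%) or runs the test two-sided, with about 83% power at a CV of 15% where 90% is stated.

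The figures assume lognormal concentrations, 20 independent patient values and an equal-tailed two-sided test. The gap between readings is material only for a true CV of roughly 15–30%. A reader might take the 54–57% as the likely chance of a false success in this trial. The documents do not support that, since they give no tumor CV and their plasma surrogate implies that both readings fail. Severity: low end of should-fix.

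**What to change.** Add to 8.4:

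> *The between-patient SD of log tumor metformin concentration (one value per patient) will be tested against 0.25 with the one-sided 5% chi-square test of 8.7. Objective 2.1 is met if the one-sided 95% upper confidence bound is below 0.25 (observed log SD of about 0.182 or less at n = 20).*

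Add to 8.6:

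> *except the one-sided test of tumor CV in 8.4.*

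One value per patient matches 8.7, which gives its n as "sample size (number of tumors and patients").

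If 8.6 is to stand without exception, name the equal-tailed two-sided test in 8.4 (cut-off about 0.171) and restate 8.7 as about 83% power at a CV of 15%, with a minimum detectable CV of about 14.3%.

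The cost is one or two sentences in 8.4 and a clause in 8.6, with no change to patients, samples or enrolment. The preferred wording keeps the 90% power and inherits the small approximation already in 8.7 (type I error about 5.8% at an exact lognormal CV of 25%).
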